6.6 Prior and concomitant medications

Prior medications will include any medications that started prior to the date of the first dose of UCB6114. This will include medications that started prior to the first dose of UCB6114 and continued after.

Concomitant medications will include medications with a start date on or after the first dose of UCB6114 and prior to the date of the last dose of UCB6114 + 30 days, and whose stop date is either missing, or on or after the date of the first dose of UCB6114. Any medications with a start date prior to the first dose of UCB6114 and a stop date after, or continued to be ongoing during the study, will also be classified as concomitant medications. Medications with a start date > 30 days after the last dose of UCB6114 will be considered as post-study medications and will not be included in the summaries of concomitant medication.

Any medication that started prior to, and stopped after the first dose of UCB6114 or continued to be ongoing during the study, will be classified as both prior and concomitant.

Any medications with missing start dates will be classified as both prior and concomitant.

Any medications with partially missing dates will be handled as described in [Section 4.2.3](#) to classify them as prior or concomitant provided that a stop date is not present or a stop date is present but prior to the first dose of UCB6114.

All medications (prior, concomitant and post-study) will be listed for the ES. Any prohibited concomitant medications, rescue medications or steroid use will be identified via a medical review and flagged in this listing.

Prior and concomitant medications (per the definitions above) will be summarized for the SS by treatment group and by WHODD Anatomical Main Group [Level 1 term text], Pharmacological Subgroup [Level 3 term text] and PT. The reported term will be included in the listing. Separate summaries will be presented for prior medications and concomitant medications. As per the definitions above, prior medications which continued into the Treatment Period will also be classified as concomitant and will be included in both summaries.

All tabulations will be sorted alphabetically by Level 1 term, alphabetical Level 3 term within Level 1 and decreasing frequency of PT in all study participants.

A glossary of all prior and concomitant medications will be presented for the SS including the Anatomical Main Group (Level 1), Pharmacological Subgroup (Level 3), PT and reported term.

Prior and concomitant medications will be presented by Gastric/GEJ-Cancer and CRC tumor type depending on the number of participants with specific tumor types.

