4.2.3 Dates and times

Partial dates may be imputed for the following reasons:

- Classification of adverse events (AEs) as treatment-emergent;

- Classification of medications recorded on the concomitant medications log as prior or concomitant;
- Calculation of time since initial diagnosis, time since completion of most recent line of anti-cancer therapy and time since progression/relapse on most recent line of anti-cancer therapy.

Imputed dates will not be shown in the listings; all dates will be displayed as reported in the database.

The following rules will be applied for partial onset/start dates:

- If only the month and year are specified and the month and year of the first dose of UCB6114 is not the same as the month and year of the start date then the 1st of the month will be used, or the date of the Screening visit if this is later (if the latter imputation results in an end date that is earlier than the start date, then the 1st of the month will be used);
- If only the month and year are specified and the month and year of the first dose of UCB6114 is the same as the month and year of the start date, then the date of the first dose of UCB6114 will be used. If this results in an imputed start date that is after the specified end date, then the 1st of the month will be used, or the date of Screening if this is later (if the latter imputation results in an end date that is earlier than the start date, then the 1st of the month will be used). If the imputed date is the same date as the date of the first dose of UCB6114 then, for AEs, the event will be regarded as treatment-emergent. For medications, the medication will be classified as concomitant;
- If only the year is specified, and the year of the first dose of UCB6114 is not the same as the year of the start date then January 01 will be used;
- If only the year is specified, and the year of the first dose of UCB6114 is the same as the year of the start date, then the date of the first dose of UCB6114 will be used. If this results in an imputed start date that is after the specified end date, then January 01, or the date of the Screening visit if this is later will be used (if the latter imputation results in an end date that is earlier than the start date, then January 01 will be used). If the imputed date is the date of the first dose of UCB6114 then, for AEs, the event will be regarded as treatment-emergent. For medications, the medication will be classified as concomitant;

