- If the onset/start date is completely missing then the onset/start date will be imputed to the date of first dose of UCB6114 and therefore, for AEs, the event will be regarded as treatment-emergent and, for medications, the medication will be classified as concomitant.

The following rules will be applied to partial end/stop dates:

- If only the month and year are specified, then the last day of the month will be used;
- If only the year is specified, then December 31 of the known year will be used;
- If the stop date is completely unknown, the stop date will not be imputed.

Note that the start date or stop date of a prior medication (partial or otherwise) should not be imputed past the Screening date - 1.

In addition to onset and stop dates, the onset and end times of AEs occurring on the day of UCB6114 infusion will be collected on the eCRF. Onset and end times may also be recorded for other AEs that do not occur on the same day as the UCB6114 infusion. The duration of AEs with onset and end times will be calculated in days and hours:minutes (hh:mm) as:

$$\text{Duration of AE} = \text{End Date and Time} - \text{Onset Date and Time}$$

In cases where only the onset and stop dates are recorded for an AE, the duration of an AE will be calculated in days as:

$$\text{Duration of AE} = (\text{Stop Date} - \text{Onset Date}) + 1$$

Note that for participants who have an AE which starts and stops on the same day, but with only a start time or only a stop time recorded, it will be assumed that their AE started from 00:00 (if no start time is recorded) and ended at 23:59 (if no stop time is recorded) on that day.

If the date of a participant's initial diagnosis is incomplete, it will be imputed to the most recent feasible date for the calculation of time since initial diagnosis as follows:

- If only the day is missing, it will be imputed to the last day of the known month;
- If the day and month are missing, it will be imputed to December 31 in the known year;
- If the date of initial diagnosis is completely missing, then time since initial diagnosis will not be calculated.

The above date imputation rules will be applied to partially missing stop dates of a participant's last prior anti-cancer systemic therapy as well as partially and completely missing dates of progression/relapse on last prior anti-cancer systemic therapy.

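### A medication with no start date but a recorded stop before the first UCB6114 dose is tabulated as concomitant, against Section 6.6's own definition (Part B and Part C SAPs)

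*SAP*

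**What the plan says.** The Part B and Part C SAPs carry the same rules in the same sections.

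- **Section 6.6, general definition.** A medication started on or after the first UCB6114 dose is concomitant if it is one "whose stop date is either missing, or on or after the date of the first dose of UCB6114". A medication started earlier is concomitant if it stopped after the first dose or was still ongoing.
- **Section 6.6, missing start.** "Any medications with missing start dates will be classified as both prior and concomitant". Nothing is said about the stop date.
- **Section 6.6, partially missing dates.** These go to Section 4.2.3, "provided that a stop date is not present or a stop date is present but prior to the first dose of UCB6114".
- **Section 4.2.3, completely missing start.** "If the onset/start date is completely missing then the onset/start date will be imputed to the date of first dose of UCB6114", with the consequence that "for medications, the medication will be classified as concomitant".
- **Section 4.2.3, month and year known, same month as first dose.** The first-dose date is tried, with a guard: "If this results in an imputed start date that is after the specified end date, then the 1st of the month will be used". A later Screening date takes precedence, subject to a further check against the end date. The rule for a start known only by year, in the year of first dose, has a parallel guard that falls back to 1 January.
- **Section 4.2.3, note on prior medications.** The start or stop date of a prior medication "should not be imputed past the Screening date - 1".

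**The concern.** A recorded stop before the first dose settles that the medication was not taken on treatment, whatever its start date. The general definition in Section 6.6 respects this. The missing-start sentence in the same section does not, and because it is specific and unconditional, a programmer would reasonably apply it as written.

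The SAP shows elsewhere that end dates matter. The partial-start rules that use the first-dose date check for an imputed start falling after the end. For adverse events, Section 8.2 drops the treatment-emergent default when there is clear evidence of an earlier start and no worsening. The rule for a completely missing medication start has no equivalent condition.

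At stake is the accuracy of the concomitant-medication summaries by treatment group and preferred term, and consistent programming across the two SAPs.

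**Working it through.** The plan gives no figure to reproduce, so the check traces one hypothetical record through the rules. The dates are assumed for illustration.

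Assumed inputs: Screening 20 Feb 2023; first UCB6114 dose 15 Mar 2023; recorded stop date 01 Feb 2023.

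1. **Start completely missing, Section 4.2.3.** The imputed start is 15 Mar 2023. From 01 Feb to 01 Mar is 28 days and from 01 Mar to 15 Mar is 14 days, so the imputed start falls 28 + 14 = 42 days after the recorded stop. No check catches this. The class is concomitant.
2. **Start completely missing, Section 6.6.** The class is both prior and concomitant, so the record enters both summaries.
3. **Start known only as 2023, Section 4.2.3.** The first-dose date (15 Mar) is tried and falls after the stop. The fallback is 01 Jan 2023 or, if later, the Screening date (20 Feb), which also falls after the stop. 01 Jan 2023 is therefore used. The start is before first dose and so is the stop, so under Section 6.6 the medication is prior only.
4. **General definition in Section 6.6.** The stop precedes the first dose, so neither route to concomitant is open.
5. **Screening minus 1 note.** Capping the imputed start at 19 Feb 2023 would override the first-dose imputation just above it in the same section. The capped start could still fall after the stop (19 Feb against 01 Feb, 18 days). The note governs dates, not classes, so the class stated in Section 6.6 is unchanged.

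| What is known of the start | Rule applied | Class |
|---|---|---|
| Nothing | Section 6.6 missing-start sentence | Prior and concomitant |
| Year only (2023) | Section 4.2.3 with end-date check | Prior only |
| Start not used, stop before first dose | Section 6.6 general definition | Not concomitant |

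The same drug with the same recorded stop changes class only because the year of its start is unknown.

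**Size in a table.** Section 2.3 gives 3 to 9 evaluable participants per dose level. If one participant's only record for a preferred term is of this type, the row changes by 1/9 = 11.1 to 1/3 = 33.3 percentage points. The tables use the Safety Analysis Set, which can also hold replaced participants. A larger denominator would make the shift smaller.

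**The case against.** The strongest defence is that counting unknown starts as concomitant is a deliberately over-inclusive convention. Long-standing drugs with an unknown start that are still ongoing are correctly classed as both. That stands wherever exposure is uncertain. It does not cover a record whose stop date shows that use ended before treatment.

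A second defence is the Screening minus 1 note, whose wording can be read to reach completely missing dates. It is relevant and would bar the first-dose imputation for such a record. It does not cancel the explicit classification in Section 6.6, so it adds a conflict and does not cure the problem.

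Three stronger readings are tempting, and the documents do not support them:

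- **That the rule feeds prohibited-medication deviations and hence the Per-protocol Set.** Section 6.6 lists all medications and flags prohibited ones by medical review. Section 4.2.3 shows dates in listings as recorded. Sections 3.4 and 3.5.3 place deviation and exclusion decisions with the specifications document and the Data Evaluation Meetings. Nothing ties these decisions to the derived class.
- **That washed-out drugs are the ones misreported.** These sections do not mention washout; they support only that the drug stopped before first dose. Prior anti-cancer therapies have their own summaries in Section 6.3.
- **That Sections 4.2.3 and 6.6 flatly disagree on the class.** Section 4.2.3 says concomitant, not concomitant only, and Section 6.6 lets the classes overlap. The wording should be aligned, but the two can be read together.

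**Conclusion.** The point holds as a contradiction within the classification rules of both SAPs. A medication with a completely missing start and a recorded stop before the first UCB6114 dose is counted as concomitant, although the definition in Section 6.6 excludes it.

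The consequence is minor. It is confined to the descriptive concomitant-medication tables, and no primary, secondary or antitumor analysis in the shown text uses this class. The shift of 11 to 33 percentage points assumes one affected participant in a group of 9 to 3. The documents do not indicate how many records will have no start date at all, not even a year, together with a known pre-dose stop. The number may be zero.

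**What to change.** In Sections 6.6 and 4.2.3 of both the Part B and Part C SAPs, make the rule for a completely missing medication start depend on the stop date, after any partial-date imputation of that stop:

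- stop before the first UCB6114 dose: prior only;
- stop missing, ongoing, or on or after the first dose: both prior and concomitant.

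Reword the medication clause of the completely-missing-start rule in Section 4.2.3 to give the same two outcomes. Reconcile the Screening minus 1 note with it, for example by limiting the note to medications classed as prior only and barring any imputed start later than the recorded stop.

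The cost is a sentence or two in each SAP and one programming condition. The over-inclusive default remains wherever on-treatment use cannot be ruled out.

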7. MEASUREMENTS OF TREATMENT COMPLIANCE

During Part B of this study, administration of UCB6114 will be performed via iv infusion at the study site under the supervision of the designated site personnel and in compliance with the Guideline for First in Human clinical studies (EMEA/CHMP/SWP/28367/07Rev. 1).

Compliance will be monitored at the site through a review of accountability logs which will be used to record UCB6114 dispensing and return information to ensure that each study participant received the correct UCB6114 dose level.

Study participant compliance with respect to the actual dose of TFD/TPI taken will be evaluated through the use of a participant diary, data from which will be transcribed onto the TFD/TPI study medication administration form in the eCRF which includes the total dose of TFD/TPI taken in the 15mg and 20mg tablets prescribed to a participant on Days 1 to 5 and Days 8 to 12 of each cycle. Percentage compliance will be calculated overall and by cycle as defined below:

Compliance (%) =

$$\frac{(\text{Actual dosage administered})}{\text{Expected dosage}} \times 100$$

Where

The actual dosage administered is calculated as the sum of the actual dose administered on Days 1 to 5 and Days 8 to 12 (inclusive) during each cycle and overall.

Expected dosage in a cycle = Prescribed total daily dose (as recorded on the eCRF) × Expected number of dosing days in a cycle.

Expected dosage overall = Prescribed total daily dose (as recorded on the eCRF) × Expected number of dosing days overall.

Expected number of dosing days in a cycle is defined as the sum of Days 1 to 5 and Days 8 to 12 (inclusive) (10 days for participants who complete a cycle or up to the last scheduled dosing day for participants who discontinue TFD/TPI during a cycle).

Expected number of dosing days overall is the number of cycles of TFD/TPI received × 10 for participants who complete dosing in all cycles up to Day 12 or, for participants who discontinue TFD/TPI during a cycle, it is the number of completed cycles of TFD/TPI received × 10 + the number of scheduled dosing days up to the discontinuation of TFD/TPI).

Note that, per protocol, intake of TFD/TPI is twice a day, every 12 hours, and the prescribed number of tablets should be taken within 1 hour of completion of morning and evening meals. In cases where the first intake on Day 1 and/or Day 8 of a cycle is delayed into the afternoon then TFD/TPI dosing in this cycle may extend into Day 6 and/or Day 13. This is acceptable and therefore all dosing days should be taken into account in the compliance calculation.

Any dosing deviations will be reviewed as IPDs at the DEMs and assessed for possible impact on the PPS and the summaries of PK endpoints. If considered important, these deviations will be included in the summary and listing of IPDs.

8. SAFETY ANALYSES

All safety summaries and listings will be presented by Gastric/GEJ-Cancer and CRC treatment group based on the SS, unless otherwise stated.

All safety summaries may be presented by tumor type depending on the number of participants with specific tumor types.

8.1 Extent of exposure

Extent of exposure to UCB6114 and TFD/TPI administered in Part B will be summarized and listed. In addition, a separate summary table and listing of participant compliance, with respect to taking TFD/TPI tablets, will be presented.

8.1.1 UCB6114

Details of UCB6114 treatment administration on Day 1 and Day 15 of each cycle of study treatment will be listed. This listing will be split into two parts. The first part will include the start and stop dates and times of infusion, duration of infusion, infusion rate, whether the infusion was temporarily stopped/interrupted, whether the infusion was permanently discontinued and, if this was the case, whether the interruption or permanent discontinuation was due to an AE or other reason. The second part of this listing will include, for each visit, infusion site, total volume delivered, volume infused, planned total dose and total dose actually administered at infusion. In addition, the percentage of planned dose received, total dose administered across all cycles, the number of complete cycles of UCB6114 received and the total number of doses of UCB6114 received will be listed.

The percentage of planned UCB6114 dose received will be calculated for each study participant at each dosing visit within each cycle as follows:

$$\text{Percentage of Planned Dose Received} = 100 \times \frac{\text{Total Dose Administered}}{\text{Planned Total Dose}}$$

Actual duration of each UCB6114 infusion will be calculated in minutes only for those study participants who did not have any temporary interruption(s) of their infusion using the infusion start and stop times and included on this listing. Length of interruption(s) will be calculated for those study participants who had temporary interruption(s) of their infusion.

The number of complete cycles of UCB6114 received (0, 1, 2, 3, 4, >4) will be summarized using frequency counts and percentages, and summary statistics will be presented for the total dose of UCB6114 received across all cycles, the total number of doses of UCB6114 received and the total duration of exposure to UCB6114.

Total duration of exposure will be calculated in days as follows:

$$\text{Total Duration of Exposure} = (\text{Date of Last Dose of UCB6114}-\text{Date of First Dose of UCB6114}) + 30$$

Note that 30 days is added to this calculation to account for a participant's continued exposure to UCB6114 following their last dose of study treatment.

Note that a participant is deemed to have completed a full cycle of UCB6114 if they receive the planned dose of UCB6114 on Day 1 and Day 15 of the cycle and a decision was not made to discontinue UCB6114 up to and including Day 28 relative to Day 1 of a cycle.

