[Part 2 of 2 of the document. The other parts are not shown.]

The purpose of this statistical analysis plan (SAP) is to provide all information that is necessary to perform the required statistical analysis of the dose escalation (combination therapy) module (Part B) of study ONC001. It also describes the summary tables, figures and listings (TFLs) to be generated for Part B according to:

Protocol amendment 6, dated 26 June 2023;

Electronic case report form (eCRF) (Clinical Data Management System [CDMS] postproduction change [CPPC] #14, version 23.0, dated 14 April 2023);

UCB's standards for TFL shells version 2023Q1;

Part A TFL shells, final version 2.4, dated 04 July 2023;

Part B and C Mocks draft version 1.4, dated 4 September 2023 (under development);

Part A, B and C List of TFLs (LoT) draft version 1.2, dated 04 July 2023 (under development);

UCB's Derivation of Efficacy Endpoints document, version 0.6, dated 21 January 2022.

Unless specified in the sections below, Part B of the study will be analyzed as described in the most recent version of the protocol. If a future protocol amendment necessitates a substantial change to the analysis of the Part B study data, this SAP will be amended accordingly. In addition, if the methodology for the analysis of key study endpoints must be modified or updated prior to the final database lock for Part B of this study, a SAP amendment will be required. Protocol amendments that do not affect the statistical analysis will not necessitate an amendment to the SAP. If, after database lock, additional analyses are required to supplement the planned analyses described in this SAP, these changes will be described in the clinical study report (CSR) together with the associated rationale.

Note that there may be a number of data cut-offs defined prior to the final database lock for Part B due to the regulatory safety reporting requirements for this study.

The content of this SAP is compatible with the International Council for Harmonization (ICH)/Food and Drug Administration (FDA) E9 Guidance (ICH-E9).

UCB is the Sponsor and ICON PLC is the contract research organization (CRO) for this study.

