8.1.2 TFD/TPI

Details of TFD/TPI treatment administration on Days 1 to 5 and Days 8 to 12 of each cycle of study treatment will be listed. The listing will include prescribed total daily dose, date of TFD/TPI administration, time of morning dose, number of 15mg and 20mg tablets taken in the morning, time of evening dose, number of 15mg and 20mg tablets taken in the evening and total daily dose administered. A separate listing of compliance to TFD/TPI treatment will be presented. This will include, overall and in each cycle, the total dosage administered, the prescribed total daily dose, expected number of dosing days, expected dosage and the percentage compliance.

Summary statistics will be presented for the total dose of TFD/TPI received across all cycles and for the total duration of exposure to TFD/TPI.

Total duration of exposure will be calculated in days as follows:

$$\text{Total duration of Exposure} = (\text{Date of Last Dose of TFD/TPI} - \text{Date of First Dose of TFD/TPI}) + 30$$

Summary statistics will be presented for overall percentage compliance, and by cycle, together with a categorical summary of the number and percentage of participants who were <80%, 80-90%, and >90% compliant with respect to taking the prescribed TFD/TPI dose.

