Separate listings of all SAEs, TEAEs leading to discontinuation of UCB6114 and TFD/TPI, TEAEs leading to discontinuation of TFD/TPI only and TEAEs leading to discontinuation of the study will also be presented.

All deaths that occur on study (defined as during study treatment or within 30 days of the last dose of UCB6114) will be listed separately. This listing will include the primary cause of death and the number of days between the date of the last dose of UCB6114 and death, defined as

$$\text{Days since last dose} = (\text{Date of death} - \text{Date of latest dose of UCB6114})$$

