$$\text{Total Duration of Exposure} = (\text{Date of Last Dose} - \text{Date of First Dose}) + 30$$

Note that 30 days is added to this calculation to account for a participant's continued exposure to UCB6114 and the components of mFOLFOX6 following their last dose of study treatment.

Note that a participant is deemed to have completed a full cycle of UCB6114 if they receive the planned dose of UCB6114 on Day 1 and Day 15 of each cycle and a decision was not made to discontinue UCB6114 up to and including Day 28 relative to Day 1 of a cycle.

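### Total duration of exposure adds 30 days after the last dose with no cap at death, last contact or data cut-off, and Part B carries the 30 days over to TFD/TPI although its stated reason covers UCB6114 only

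*SAP*

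**What the plan says.** Part B SAP, Section 8.1.1, computes total duration of exposure to UCB6114 in days as the last dose date minus the first dose date, plus 30. It explains that the 30 days stand for a participant's "continued exposure to UCB6114 following their last dose of study treatment".

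Part B SAP, Section 8.1.2, uses the same construction for TFD/TPI; the formula ends "Date of First Dose of TFD/TPI}) + 30". No reason is given there. The same section places intake on Days 1 to 5 and Days 8 to 12 of each cycle, and Section 7 counts 10 dosing days in a completed cycle.

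Part C SAP, Section 8.1, applies one formula with the same 30 days to UCB6114 and to each mFOLFOX6 component. Here the reason is widened to "continued exposure to UCB6114 and the components of mFOLFOX6 following their last dose of study treatment".

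None of these sections shortens the interval for death, last contact or a data cut-off, and no other section shown does so. Yet both situations are provided for. Part B Section 8.2 has a listing of on-study deaths, "defined as during study treatment or within 30 days of the last dose of UCB6114", and the Introduction says that "there may be a number of data cut-offs defined prior to the final database lock for Part B". Part C has matching text. For counting completed cycles, Section 5.1 of both SAPs has a rule for participants who are ongoing at a cut-off; for exposure there is none.

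**The concern.** There are two separate faults.

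First, a rule followed exactly should not return impossible values. A 30-day tail is a legitimate convention for UCB6114, but it can describe exposure only while the participant is alive and, at an interim delivery, only up to the date the data reach. As written, the programmer must credit days after death or after the cut-off.

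Second, the Part B reason for the tail is about UCB6114, yet the tail is attached to TFD/TPI as well. For TFD/TPI, Section 8.1.2 summarizes total dose, compliance and this duration, so the duration is the only summary there that is measured in days. Compliance does not correct it, because under Section 7 the expected dosing days stop when TFD/TPI is discontinued. A participant who stops after one day can show full compliance and 30 days of exposure.

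At stake is whether the exposure table describes what participants received. Dose levels are small (3 to 9 evaluable participants, Section 2.3), so one such participant can move a group's summary.

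**Working it through.** The SAP gives no worked exposure figure, so there is nothing to reproduce. The check is date arithmetic on the stated formulas.

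**Inputs.** UCB6114 is given on Days 1 and 15 of each 28-day cycle (Part B Section 3.2.3). TFD/TPI is taken on Days 1 to 5 and 8 to 12 (Sections 7 and 8.1.2). The added constant is 30 (Sections 8.1.1 and 8.1.2; Part C Section 8.1). The dates of death and cut-off below are illustrations, not SAP figures.

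**Formulas.**
- SAP duration: (last − first) + 30
- Calendar span: (last − first) + 1
- Capped duration: min[(last − first) + 30, (end − first) + 1], where end is the date of death, last contact or cut-off

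Counting the first dose date as a day of exposure, the SAP interval ends 29 days after the last dose. If follow-up ends d days after the last dose, with d below 29, the excess is 29 − d days.

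**Missing cap, UCB6114 on Days 1 and 15.** The SAP duration is (15 − 1) + 30 = 44 days in every row.

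| Death or cut-off, days after last dose | SAP | Capped | Excess |
|---|---|---|---|
| 0 | 44 | 15 | 29 |
| 5 (Day 20) | 44 | 20 | 24 |
| 10 | 44 | 25 | 19 |
| 20 | 44 | 35 | 9 |
| 29 | 44 | 44 | 0 |

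A single infusion with death on Day 8 gives 0 + 30 = 30 days against 8 lived. A last dose the day before a cut-off (d = 1) gives 29 − 1 = 28 days beyond it.

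**Effect on a group mean.** One participant with a 24-day excess raises the mean by 24/9 = 2.7 days in a group of 9 and by 24/3 = 8 days in a group of 3.

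**TFD/TPI tail.**
- One cycle, Days 1 to 12: (12 − 1) + 30 = 41 days, against a 12-day span with 10 dosing days.
- Two cycles, Day 1 to Day 40 (28 + 12): (40 − 1) + 30 = 69 days, against a 40-day span with 20 dosing days.
- One day of tablets: 0 + 30 = 30 days against 1.

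The tail does not align TFD/TPI with the TEAE window either. That window runs to 30 days after the last dose of UCB6114 (Section 8.2). After one full cycle the TFD/TPI interval ends on Day 41, whereas the TEAE window ends on Day 15 + 30 = Day 45.

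**Part C example.** Oxaliplatin on Days 1 and 15 gives 44 days against a 15-day span.

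**Effect of the constant on comparisons.** Using + 30 instead of + 1 adds 29 days to every participant. Means, medians, minima and maxima all rise by 29; standard deviations and absolute differences between dose levels do not change.

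**The case against.** The strongest reply is that this is a declared convention in a descriptive table, surrounded by outputs that show the truth. Much of that stands.

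- **The UCB6114 tail.** Its reason is stated and it lies close to the TEAE window, the Safety Follow-up Period and the on-study death window. The 30 days are not the fault for UCB6114; the missing cap is.
- **Neighbouring outputs.** Part B Section 8.1.1 also summarizes complete cycles, number of doses and total dose. Someone with one infusion who dies on Day 8 appears with no complete cycle and one dose, and in the death listing. Part C summarizes doses and total dose for each component. This limits the harm but does not make days after death a valid value.
- **Cut-offs.** These serve safety reporting before final lock, and Part B ends only with the last participant's Final Visit. The overrun past a cut-off is therefore essentially a matter for interim deliveries. The overrun past death remains at final analysis.
- **The TFD/TPI comparison.** The 12 days are a calendar span, and the cycle itself lasts 28 days, so other comparators are possible. Last minus first plus 1 is also a convention: it counts rest days between cycles but not those after the last intake. Even so, the plan offers no reason for 41.

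A reader might infer more than the text supports. One might think the 30 days compress differences between dose levels; as a constant it shrinks only ratios, and no ratio of exposures is planned. One might think the TEAE results are distorted; they are reported as numbers and percentages of participants and as event counts, and the one event rate in Section 8.2 (by treatment-emergent ADA positivity) has no stated denominator. One might call 30 days wrong for the mFOLFOX6 components; that needs elimination data which the document does not give. Part C asserts continued exposure to them, and all that can be said is that the assertion is unsupported.

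**Conclusion.** The point holds as a fault in a descriptive summary. Followed as written, the formula credits exposure after death or cut-off whenever either falls fewer than 29 days after the last dose, by 29 − d days (24 of 44 days in the Day 20 example). How many participants this touches cannot be known from the plan; it depends on how many die, leave the study or are cut off in that interval. In Part B the tail lengthens every TFD/TPI duration by 29 days relative to the intake span, without a reason that applies to that drug. The arithmetic assumes scheduled dosing days and counts both end dates. The change is worth making because it is specific and nearly free. It is not a threat to the primary safety endpoints.

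**What to change.** State the same rules in both SAPs:

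- **UCB6114:** min[(last dose − first dose) + 30, (earliest of death, last contact or data cut-off − first dose) + 1].
- **TFD/TPI (Part B):** (last dose − first dose) + 1, with the same cap, since the stated reason for the tail does not cover it.
- **mFOLFOX6 components (Part C):** apply the same cap, and either support the 30-day tail for each component or report (last dose − first dose) + 1.

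Write the UCB6114 cap on the duration, as above. Capping the end date at last dose + 30 and then adding 1 would give (last − first) + 31 for uncapped participants, a day longer than the plan intends. Also say whether last contact applies only to participants who have left the study, so that those ongoing at an interim delivery are capped at the cut-off date.

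The cost is formula wording and a few lines of analysis-dataset code, with no new data: Section 10.1.1 already uses dates of death and last contact. UCB6114 exposure becomes shorter only for capped participants; TFD/TPI exposure becomes 29 days shorter wherever a cap would not already have shortened it.
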